Study Title: Persistence of Glaucoma Patients With Web-Browser-Based Visual Field Test

Principal Investigator: [name]

NCT Number: NCT05690152

Unique Protocol ID: 202207403

IRB ID: 202207403

Date: 9/5/2025

Web Browser Visual Field Study

PI: [name]
IRB ID #: 202207403

Project Details

I. Project Introduction

I.1

Project to be reviewed by:
IRB-01

I.2

Project Title:
Visual Field Telemedicine in Glaucoma Patients using a Web Browser-Based Test Strategy

I.3

Short Title (optional):
Web Browser Visual Field Study

I.4

Provide a short summary of the purpose and procedures of the study proposed in this IRB application.

- DO NOT include information on studies not proposed in this application.***
- Use LAY terminology only. This must be easily understandable by IRB community members and nonscientists.***
- DO NOT cut and paste technical abstracts from funding applications that may not be understood by a general audience.***

The purpose of this prospective study is to determine the reliability of and patient compliance with a testing strategy with a novel home, web-based visual field test, EyeSimplify (M&S Technologies, Niles, IL), for purposes of surveilling glaucomatous progression. In this study, EyeSimplify will be compared to the current accepted gold standard Standard Automated Perimeter, the Humphrey Visual Field Analyzer (Carl Zeiss Meditec Inc., Dublin, CA).

The proposed study will be conducted at the University of Iowa Hospitals and Clinics and via telemedicine encounters. We estimate 50 subjects will be recruited to participate in the study. Data collected will not include patient identifiers.

Research involves retrospective collection of data, documents, and records, as well as prospective collection of visual field testing performance. The source of data will be retrospective review of computerized or written medical record and testing conducted in clinic beginning upon IRB approval. Patients with suspected, mild, moderate, or severe glaucoma will be included. Clinical data including age, gender, ethnicity, visual acuity, intraocular pressure, severity of disease, Humphry Visual Field performance, EyeSimplify Visual Field performance, and satisfaction survey will be recorded.

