Following study recruitment, subjects will be asked to take EyeSimplify visual field tests at home biweekly for six months. They will have no additional responsibilities between tests. Subjects will access the EyeSimplify web browser on their personal electronic devices using a link and login credentials provided to them by a research assistant. Upon logging into the EyeSimplify web browser, subjects will click the "Start Test" button found along the left side of the window and follow the prompts presented on screen to calibrate their screen. Screen calibration involves holding a driver's license/credit card/ID to the screen to ensure the test window is the appropriate dimensions. Following screen calibration, subjects will follow the test prompts presented on screen to complete their visual field test. Test results are automatically sent to the research assistant who issued the exam, so subjects may exit the browser after each test. Upon study completion, subjects will be asked to fill out a brief satisfaction survey.

M&S Technologies is the developer of the EyeSimplify web-based visual field test. [name], [name], and [name] have no financial or intellectual relationship with M&S Technologies, aside from the current study and an additional study under IRB review investigating the Pico Virtual Reality Headset visual field test.

As the developers of the web-based visual field test, M&S Technologies maintains a secure, encrypted, HIPAA-compliant database of EyeSimplify users. This database includes patient profiles containing unique patient IDs (de-identified), birth year, and visual field testing results. Outside of this testing information, M&S Technologies does not have access to any additional patient information.

I.5

Specify your research question(s), study aims or hypotheses (do not indicate "see protocol")
Aim 1: Determine test reliability of the EyeSimplify (M&S Technologies, Niles, IL) home, web-based visual field test in glaucoma patients.
Aim 2: Determine the concordance of EyeSimplify to the Humphrey Visual Field Analyzer (Carl Zeiss Meditec Inc., Dublin, CA) in identifying visual field loss progression.
Aim 3: Determine patient compliance with and tolerance of biweekly EyeSimplify testing for a 6 month period, assessed by test recordkeeping and a patient experience survey.

Primary Hypothesis: The EyeSimplify visual field test will produce reliable visual field testing data.

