Secondary Hypothesis: The EyeSimplify visual field test will be non-inferior to the Humphrey Visual Field Analyzer in identifying glaucomatous progression trends.

I.6

Background and significance and/or Preliminary studies related to this project. (do not indicate "see protocol")
Glaucoma is the leading cause of irreversible blindness worldwide (1-2). Standard Automated Perimetry is the current accepted standard for diagnosis and monitoring of glaucomatous visual field loss (3), and the Humphrey Visual Field Analyzer (HFA; Carl Zeiss Meditec Inc., Dublin, CA) is the automated perimeter that is most frequently used due to it currently having the largest market share. The HFA is a useful clinical tool; however, it is a large, expensive device. Testing takes approximately seven minutes per eye when using the Swedish Interactive Threshold Algorithm (SITA) Standard testing algorithm, and testing is typically only done at 6-12 month intervals. Recently, there has been interest in the development of alternative methods to monitor visual field progression outside of the clinic setting (4). EyeSimplify (M&S Technologies, Niles, IL) is a web-based visual field test that aims to increase the frequency at which patients can test their visual fields, improve accessibility to visual field testing, and potentially identify visual field loss progression more quickly.

I.7

Literature cited / references (if attaching a grant or protocol enter N/A).
1. Quigley HA. Number of people with glaucoma worldwide. Br J Ophthalmol. May 1996;80(5):389-93. doi:10.1136/bjo.80.5.389

doi:10.1136/bjo.2005.081224

II. Research Team

II.1

Principal Investigator

Name	E-mail	College
[name]	[contact]	Carver College of Medicine

II.2

Team Members

UI Team Members

Name	E-mail	College	Contact	Key Prsn	UI COI	VAMC COI	Consent Process Involvement	Deactivated
[name]	[contact]	Carver College of Medicine	Yes	Yes	No		Yes	No

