- Describe study populations separately if they will be participating in different procedures - include CONTROL population if applicable.*
- DESCRIBE:**
- *What subjects will be asked to do/what happens in the study (in sequential order)*
 - *The time period over which procedures will occur*
 - *The time commitment for the subject for individual visits/procedures*
 - *Long-term followup and how it occurs*
- Potential subjects will be approached at the time of their regularly scheduled appointment to participate in this research study. The research assistant will answer any questions potential subjects may have regarding the purpose, procedure, and risks of the study. If they agree to participate, subjects will sign an informed consent.
- In addition to routinely scheduled clinical examination, including visual field testing (VF) with the Humphrey Field Analyzer (HFA), subjects will be asked to complete biweekly VF for six months using EyeSimplify, a novel, web-based VF, at home. Subjects will be instructed to complete the EyeSimplify VF in a quiet, dark room free of distractions. The research assistant will be available via email or telephone to troubleshoot any issues that may arise.
- The EyeSimplify uses a 24-2 examination protocol with a Neighborhood-Zippy Estimation by Sequential Testing (ZEST) testing algorithm. Background brightness will be set to 15.8 ASB. The test will use a scaled white stimulus. Subjects will self-administer the EyeSimplify VF at home. The EyeSimplify VF will be deemed unreliable if FP >15%. The HFA uses a 24-2 examination protocol with a SITA standard testing algorithm. A clinical technician will administer the HFA VF at the University of Iowa Hospitals and Clinics' Glaucoma clinic. The HFA VF will be deemed unreliable if FP >15%. At the conclusion of the study, subjects will complete a satisfaction survey regarding testing using the EyeSimplify VF.
- VII.E.7** *Will you attempt to recontact subjects who are lost to follow-up?*
Yes
- VII.E.8** *Describe - any procedures need to be included in the consent:*

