- Electronic records (computer files, electronic databases, etc.) - All electronic files will be kept as files on an encrypted, password-protected UIHC Department of Ophthalmology network server. There will be no identifiers or link available on any transferred data; therefore, there will be no way to compromise patients' privacy or confidentiality.
 - Name - [name]
 - Title - Senior IT Support Consultant
 - University Job Classification - Faculty/Staff
- Paper/hard copy records (hard copy surveys, questionnaires, case report forms, pictures, etc.) - Informed consent documents will be transported directly from the UIHC Glaucoma clinic to a locked file cabinet in the PI's office within the Department of Ophthalmology and Visual Sciences immediately following the study recruitment clinical encounter by the PI or research assistant. These documents will remain in this locked cabinet for the duration of the study.

X.5 Do the confidentiality protections indicated above allow only members of the research team to access the data/specimens?

No

X.6 Describe

M&S Technologies, the developers of the EyeSimplify web-based visual field test, maintain a secure, encrypted, HIPAA-compliant database of patient testing information. This database includes study ID (de-identified), birth year, and experimental visual field testing data. M&S Technologies does not have access to any additional patient information.

X.7 Does your study meet the NIH criteria for a [Certificate of Confidentiality](#) or will you be applying for Certificate of Confidentiality?

No

XI. Data Analysis

XI.1 Describe the analysis methods you will use, including, if applicable, the variables you will analyze

Variables: Clinical data including age, gender, ethnicity, Humphry Visual Field performance, EyeSimplify Visual Field performance, and satisfaction survey will be collected and analyzed.

Data analysis: Humphrey Visual Field Guided Progression Analysis (GPA) and EyeSimplify Visual Field mean deviation linear trending will be compared using Bland-Altman analysis.

XI.2 Provide the rationale or power analysis to support the number of subjects proposed to complete this study.

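### Section XI.1 applies Bland-Altman analysis to fitted trends without allowing for their sampling error; unless test noise is low or true slopes vary widely, six-month limits of agreement barely separate a perfect home test from one blind to progression

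*Combined protocol and SAP*

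**What the plan says.** Aim 2 (section I.5) is to "Determine the concordance of EyeSimplify to the Humphrey Visual Field Analyzer" in identifying progression, and the secondary hypothesis is non-inferiority for progression trends. The only analysis offered is in XI.1: "Humphrey Visual Field Guided Progression Analysis (GPA") and "EyeSimplify Visual Field mean deviation linear trending will be compared using Bland-Altman analysis". XI.1 does not say which GPA output is used, in what units, or over what period.

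On the home side, "subjects will be asked to take EyeSimplify visual field tests at home biweekly for six months" (I.4). On the HFA side, fields come from routine care, where "testing is typically only done at 6-12 month intervals" (I.6). Section I.4 adds that "Research involves retrospective collection of data, documents, and records", so older HFA fields may be available, but no look-back period is given. On size, "We estimate 50 subjects will be recruited to participate in the study". XI.2 supports this only by citing a similar study that analysed 20 of 47 recruits.

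The documents give no test-retest SD, expected rate of progression, acceptable limits of agreement or non-inferiority margin, and no model that separates slope error from device disagreement.

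**The concern.** Each point on the planned plot is a fitted slope, which is an estimate with its own standard error. The variance of the home-minus-HFA difference is the true disagreement between devices plus the squared standard errors of both slopes. Limits of agreement carry the whole sum. Over six months the slope-error part can be much larger than any plausible disagreement.

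Two misreadings are then open. Wide limits may be taken as poor concordance when they mostly reflect a short series. Or a mean difference near zero may be taken as concordance although the home test tracks no individual's progression. A sloping cloud on the plot may also be taken as device bias when it only reflects which slope is less precise.

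**Working it through.** **The plan's own figure.** The sample size of 50 has no inputs behind it, so it cannot be reproduced. The only arithmetic to check is the cited precedent: 20/47 = 42.6%, which agrees with the 43% in XI.2.

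**Inputs from the documents.** Biweekly home testing for six months, read as every two weeks: 13 tests at weeks 0 to 24. Routine HFA at 6-12 month intervals. 50 subjects.

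**Assumptions, because the documents are silent.** Both trends are slopes in dB/year. Home noise is 1 dB (range 0.5 to 2) and HFA noise 1 dB. The SD of true slopes (τ) is 0.5 dB/year (also 1). The base HFA series is seven six-monthly fields over 3 years; shorter series are also tried. A perfect home test has the same true slope as the HFA plus ordinary noise. A blind one has a true slope of zero in everyone.

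**Step 1: slope standard errors.** SE = noise SD / √Σ(t − t̄)².
- Home: Σ = 182 × (2/52.18)² = 0.2674, so SE = 1/√0.2674 = 1.93 dB/year and SE² = 3.740.
- HFA, seven fields: Σ = 28 × 0.5² = 7, SE = 0.378, SE² = 0.143.
- HFA, three fields over one year: Σ = 0.5, SE = 1.41, SE² = 2.
- HFA, two fields six months apart: Σ = 0.125, SE = 2.83, SE² = 8.

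**Step 2: limits of agreement, base case.**
- Perfect: 1.96 × √(3.740 + 0.143) = ±3.86.
- Blind: 1.96 × √(3.740 + 0.143 + 0.25) = ±3.98, which is 3% wider.
- Slope error makes up 3.883/4.133 = 94% of the blind test's variance.

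| Home noise | τ | HFA series | Perfect | Blind | Gap |
|---|---|---|---|---|---|
| 2 dB | 0.5 | 7 fields | ±7.62 | ±7.68 | 1% |
| 1 dB | 0.5 | 7 fields | ±3.86 | ±3.98 | 3% |
| 0.5 dB | 0.5 | 7 fields | ±2.04 | ±2.26 | 11% |
| 0.5 dB | 1.0 | 7 fields | ±2.04 | ±2.83 | 39% |
| 1 dB | 0.5 | 3 fields | ±4.70 | ±4.80 | 2% |
| 1 dB | 0.5 | 2 fields | ±6.72 | ±6.79 | 1% |

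**Step 3: can 50 subjects show that gap?** The 95% CI of a limit is ±√(1/50 + 1.96²/98) = ±24% of its value. In the base case the variance ratio is 4.133/3.883 = 1.064. A one-sided 5% chi-square test on 49 degrees of freedom, with error variance taken as known, has power of about 10%. At 0.5 dB noise and τ = 1 it has about 94%.

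**Step 4: the mean-difference line.** A blind test shifts it by the cohort's mean true slope. Assuming −0.5 dB/year, the base case gives z = 0.5/(2.033/√50) = 1.74 and power Φ(1.74 − 1.96) = 41%. At 0.5 dB home noise the power is 87%. If only 20 subjects are analysed, as in the precedent, base-case power is about 20%.

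**Step 5: trend of difference on mean, perfect test.** Correlation = ½(SE²home − SE²HFA) / √[(SE²home + SE²HFA)(τ² + (SE²home + SE²HFA)/4)].
- Seven HFA fields: 1.799/√(3.883 × 1.221) = +0.83.
- Three fields: +0.28.
- Two fields: −2.130/√(11.740 × 3.185) = −0.35.

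With seven fields a blind test gives +0.81, so the trend does not discriminate either.

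**Step 6: does another analysis use the data better?** The correlation of the two fitted slopes is a simple stand-in for the joint model. For a perfect test it is 0.25/√(3.990 × 0.393) = 0.20; for a blind test it is 0. By Fisher's z with n = 50, one-sided 5% power is Φ(0.202 × √47 − 1.645) = Φ(−0.26), or about 40%. At 0.5 dB home noise the correlation is 0.37 and power about 84%. Comparing variances gives about 10% and 29% in the same two cases.

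**The case against.** The strongest reply is that the difficulty lies in the six-month design, not in Bland-Altman, and that wide limits correctly say a six-month home slope cannot replace an HFA slope. That is a fair reading if interchangeability of single slopes is the question. But Aim 2 asks about concordance in identifying progression, and the limits alone do not answer that. Nor is the information the same under every method: step 6 shows that the covariance between devices carries signal that the limits largely lose.

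Other parts of the reply stand and restrict the point.
- A reader might infer that the limits measure sampling error instead of disagreement. They contain both; the issue is which dominates, and that depends on SDs the documents do not give.
- A reader might infer that the whole Bland-Altman result is the same for a perfect and a blind test. Step 4 shows that the mean line may reveal a blind test if noise is low and the mean slope is clearly non-zero. It still does not measure individual concordance: a test returning the group-average slope for everyone has zero bias and tracks no one.
- A reader might infer that a strong positive proportional bias is bound to appear. Its size and sign depend on the HFA series, which the plan leaves open.
- If biweekly means twice a week, 52 tests halve the home slope error to 0.96 dB/year. With 1 dB noise, τ = 0.5 and six HFA fields over 2.5 years, the limits become ±2.11 and ±2.33, a 10% gap.
- Slope against slope is itself a reading of XI.1, since the GPA output is not named.

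Aim 2 also serves the secondary hypothesis, not the primary one.

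**Conclusion.** The point holds conditionally. XI.1 makes no allowance for slope error. On the slope-against-slope reading with two-weekly tests, the limits are dominated by that error unless within-patient noise is well below about 1 dB or true slopes vary widely. Under the base assumptions the limits of a perfect and a blind test differ by 3%, against a sampling uncertainty of ±24% in each limit. A short HFA series does not remove the problem (gap 1% to 2%). In the favourable corner, 0.5 dB noise with slope SD 1, the gap is about 39% and would usually be seen with 50 subjects.

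The documents do not support the stronger conclusion that Aim 2 must be answered wrongly. They support the narrower one that the planned output is hard to interpret without the slope errors, and that a difference-mean trend should not be read as device bias. All figures assume full 13-test series and, where older HFA fields are used, a true slope that is constant over the HFA look-back and the study.

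**What to change.** In XI.1, make the Aim 2 analysis a linear mixed model of the individual mean-deviation values from both devices against test date, including the retrospective HFA fields. Give each device its own random slopes, correlated between devices, and its own residual variance. Report the mean slope difference and the correlation of true slopes, each with a confidence interval. State the look-back period and the assumed noise and slope SDs.

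If a Bland-Altman plot is kept, name the GPA output as a slope in dB/year. Print beside the observed limits those expected from slope error alone, ±1.96 × √(mean SE²home + mean SE²HFA). Use HFA slope standard errors only for subjects with at least three fields, because two leave no residual degrees of freedom.

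Claim concordance only if the confidence interval supports it; otherwise state that it is not estimable over six months.

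The cost is a little more programming, with no new visits or subjects. The downside is that the interval may be wide. The study was closed with the IRB in September 2025, so the change now applies to analysis for reporting. It is feasible if the de-identified file keeps the timing of each test.
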